4.2.4 Progression-Free Survival

Investigator-assessed PFS will be analyzed as a secondary endpoint. A progression event is defined as radiological evidence of progression, significant clinical symptomatic progression, or the need to introduce a non-study drug therapy. Subjects who do not experience those events will be censored based on the scheme in Table 4.2.4-1.

Table 4.2.4-1: Censoring Scheme Used in the Analysis of PFS

Situation	Date of Progression or Censoring	Outcome
No baseline tumor assessments	First dose	Censored
No on study tumor assessments and no death	First dose	Censored
Progression documented between scheduled visits (per RECIST 1.1 criteria or clinical)	Date of the first documented tumor progression	Progressed
No progression, no death	Date of last tumor assessment with no documented progression	Censored
New anticancer treatment started without a prior reported progression	Date of initiation of the subsequent anti-cancer therapy	Progressed
Death without progression and without subsequent anti-cancer therapy	Date of death	Progressed

PFS = (date of event/censoring - first dose date) / 30.4375 (months).

4.2.5 Objective Response Rate

Overall Response will be assessed by the investigator at clinic visits with scheduled Tumor Assessments and will be assessed according to RECIST 1.1 criteria. These criteria allow for a standard overall assessment to be made based on the status of Target Lesions, Non-Target Lesions, and New Lesions. The overall response is assessed on a nominal categorical scale as one of five responses:

- 1) Complete Response (CR)
- 2) Partial Response (PR)
- 3) Stable Disease (SD)
- 4) Progressive Disease (PD)
- 5) Not Evaluable (NE)

The ORR is defined as the number of subjects with a best overall response (BOR) of a complete response (CR) or partial response (PR) divided by the number of all treated subjects. BOR is defined as the best response designation, recorded between the date of first dose and the date of the initial objectively documented tumor progression by the investigator or the date of subsequent therapy, whichever occurs first. For subjects without documented progression or subsequent therapy, all available response designations will contribute to the BOR determination.

The Duration of Objective Response (DOR) is a related secondary endpoint in the study. For subjects achieving an overall response of CR or PR, DOR is calculated as the length of time from the initial PR/CR until the first overall response of PD or death due to any cause, whichever

occurs first. Subjects achieving PR/CR who never progress nor die will be censored on the date of their last tumor assessment.

Time to Objective Response (TTR) is defined as the time from the start of treatment to the date of the first documented response (CR or PR). TTR will be evaluated in all treated subjects and for responders (i.e. subjects with a BOR of CR or PR).

5 SAMPLE SIZE AND POWER

Of 768 subjects who will be screened to receive first-line therapy for advanced disease with histologically confirmed stage III (unresectable) or stage IV melanoma, approximately 615 subjects will be treated with nivolumab and ipilimumab regimen. This sample size is based on the primary objective of the study: determining the incidence of high-grade (CTCAE v4.0 Grades 3-5), treatment-related, select adverse events of potentially immune-mediated etiology in subjects receiving first-line therapy for advanced disease. The sample size will allow for estimating an incidence of about 50% with a 95% CI of (46.06%, 54.11%) under 308 subjects with events among 615 treated subjects.

6 STUDY PERIODS, TREATMENT REGIMENS AND POPULATIONS FOR ANALYSES

6.1 Study Periods

While the study is described in Section 2.1 as consisting of three phases including Screening, Treatment, and Follow-up, for the description of the planned statistical analyses, there are two pertinent study periods that will be defined: the Baseline period and the Post-baseline period. These are described in detail in Section 6.1 of the CA209 Core Safety SAP version 5.

6.2 Treatment Regimens

This study is comprised of only a single treatment regimen as described in Section 2.1. Treatment consists of ipilimumab / nivolumab combination treatment once every 3 weeks for 12 weeks (4 cycles total), followed by nivolumab monotherapy every 2 weeks for up to 24 months from first combination dose (Part I and Part II). Subject may be treated for more than 24 months for a maximum of 50 cycles in case an on-hold period occurs during the treatment phase.

6.3 Populations for Analyses

The following analysis populations are defined for this study:

- Enrolled subjects: All subjects who signed the informed consent form and obtained a subject number.
- Treated subjects: All subjects who received any study treatment. This is the primary population for safety and efficacy analyses.

- Response evaluable subjects: All treated subjects who have baseline and at least one on-study evaluable tumor measurement.

6.4 Subgroups for Analyses

The study will include several analyses performed according to subgroups of these populations. These subgroups are summarized below. Except for subject enrollment, healthcare resource utilization, outcome research, and PD-L1 expression, all analyses will be performed for all treated subjects and for each subgroup defined in this section.

- ECOG PS subgroups: Subjects will be classified into subgroups based on their baseline ECOG PS grade (0-1 vs 2).
- Brain Metastasis subgroup: Subjects will be grouped into brain metastasis at baseline.
- Disease Subtype subgroup: Subjects will be classified into subgroups based on their disease subtype at baseline (Ocular/Uveal, Mucosal, Cutaneous, Acral, and Other).

In addition, OS will be analyzed based on the following subgroups:

- Best Overall Response subgroups: Subjects will be classified into two subgroups based on their BOR (BOR = CR, PR, SD vs. BOR = PD, NE).

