For Part I, nivolumab and ipilimumab are administered every 3 weeks for 4 doses (Table 5.1-2). If subjects discontinue therapy during Part I, nivolumab monotherapy can be continued as

described in [Section 4.5.5](#). **For Part II**, nivolumab monotherapy is administered every 2 weeks ([Table 5.1-3](#)) until 24 months after the first combination dose (Part I and II). Subjects may be treated for more than 24 months for a maximum of 50 cycles in case an on-hold period occurs during the Treatment Phase.

Windows for dosing of both Part I and Part II are discussed in [Section 4.5](#).

An initial tumor assessment is to be completed at Week 12 (± 5 days) after the first treatment dose. Further tumor assessments are recommended to be completed as required by local standards of care or at the investigator's discretion and are recommended every 8 weeks until documented tumor progression.

Subjects treated with the study drugs will be permitted to continue treatment beyond initial PD as assessed by the investigator's clinical judgment and local standards of care as long as they meet the criteria specified in [Section 4.5.8](#).

The Treatment Phase ends when the subject is discontinued from study therapy. For a complete list of reasons for treatment discontinuation, see [Sections 3.5](#) and [4.5.6](#).

The Follow-up Phase begins when the decision to discontinue a subject from study therapy is made (no further treatment with study therapy) ([Table 5.1-4](#) and [Table 5.1-5](#)):

- Subjects who discontinue therapy in Part I are recommended to be followed by direct contact (office visit) every 4 weeks for up to 100 days after the last dose of combination regimen therapy. After completion of the onsite follow-up visits (for up to 100 days), subjects will be followed every 24 weeks ± 2 weeks for survival either by direct visit or via telephone contact. OS will be followed from the start of therapy up to 2 years or until death, withdrawal of study consent, or lost-to-follow-up, whichever comes first.

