8.4 Analyses

Descriptive statistics will be presented for each of the endpoints. The analysis of primary, secondary, and exploratory endpoints will be reported for the full safety analysis set (all treated subjects) and by subgroups based on ECOG PS, brain metastasis, ocular and mucosal melanoma, and investigator experience in treating with the nivolumab plus ipilimumab combination regimen.

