4.2.3 Overall Survival

OS will be until death, withdrawal of study consent, or lost to follow-up for up to 2 years from the first dose of study treatment. OS is defined as the time between the start of treatment and the date of death due to any cause. A subject who has not died will be censored at last known date alive. $OS = (\text{date of death/last known date alive} - \text{first dose date})/30.4375$ (months).

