7.5 Efficacy

7.5.1 Secondary Analyses

7.5.2 Survival

Overall Survival (OS) and Progression-Free Survival (PFS) will each be summarized using the Kaplan-Meier method. Median values of OS and PFS, along with two-sided 95% confidence intervals using the Brookmeyer and Crowley method will be calculated and presented. Corresponding Kaplan-Meier curves will be produced for OS and PFS based on all treated subjects and subgroups defined in Section 6.4.

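### Overall survival is split by best overall response but counted from first dose with no landmark, so guarantee time inflates the displayed gap

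*SAP*

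**What the plan says.** SAP 6.4 lists subgroups by ECOG performance status, brain metastasis and disease subtype, all fixed at baseline. For OS alone it adds one that is not: "Subjects will be classified into two subgroups based on their BOR (BOR = CR, PR, SD vs. BOR = PD, NE".

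The other pieces are:

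- **Time origin (SAP 4.2.3):** "OS is defined as the time between the start of treatment and the date of death due to any cause". Follow-up for OS runs to 2 years from first dose.
- **Output (SAP 7.5.2):** "Corresponding Kaplan-Meier curves will be produced for OS and PFS based on all treated subjects and subgroups defined in Section 6.4", together with "Median values of OS and PFS, along with two-sided 95% confidence intervals".
- **When response is recorded (SAP 4.2.5):** "BOR is defined as the best response designation, recorded between the date of first dose" and first progression or subsequent therapy.
- **First scheduled scan (Protocol 3.1):** "An initial tumor assessment is to be completed at Week 12", with a window of 5 days either side.
- **Population (SAP 6.3):** all treated subjects, whether or not they were ever scanned.

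Protocol 8.4 describes the analyses as descriptive ("Descriptive statistics will be presented for each of the endpoints"), and its subgroup list does not include best overall response (BOR). No test or hazard ratio between the two BOR groups is planned. SAP 4.2.3, 6.4 and 7.5.2 are readable, and they contain no landmark, time-dependent method or caveat for this split.

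**The concern.** Group membership is decided after the survival clock has started. To be classed CR, PR or SD, a subject must live long enough to have a qualifying scan, normally about 12 weeks. A subject who dies before any scan cannot be CR, PR or SD, and in a two-way split of all treated subjects that leaves PD/NE. The CR/PR/SD curve is thus almost flat for its first 12 weeks, while the PD/NE curve takes most of the early deaths.

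Subjects with PD on the Week 12 scan have also survived to that scan. The distortion comes mainly from pooling deaths before any assessment with true progression.

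At stake is the reading of two curves and two medians with confidence intervals. They will look like evidence of how strongly response goes with survival, and a reader has no way to separate the artefact from a real association.

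**Working it through.** The plan states no figure for OS by BOR. Its only precision statement concerns the primary endpoint: 308 of 615 gives an exact (Clopper-Pearson) interval of 46.06% to 54.11%, which reproduces and does not bear on this point. The size below therefore rests on stated assumptions.

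**Inputs from the documents.** First scan at day 84, so t0 = 84/30.4375 = 2.76 months; 615 treated; OS from first dose; OS follow-up to 24 months.

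**Assumptions.** Exponential OS with median m months, so S(t) = exp(−ln 2 · t/m) and S0 = S(t0). A fraction p of those alive at the scan are CR/PR/SD. In the null case response is unrelated to survival and there are no scans before Week 12.

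**Formulas under the null.**

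- CR/PR/SD curve for t > t0: S(t)/S0
- PD/NE curve for t > t0: (1 − p) · S(t)/(1 − p · S0)

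**Worked example, m = 24 and p = 0.6.** S0 = 0.9234.

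- At 12 months, S = 0.7071. CR/PR/SD = 0.7071/0.9234 = 76.6%. PD/NE = 0.4 × 0.7071/(1 − 0.6 × 0.9234) = 63.4%. False gap 13.2 points.
- At 24 months, S = 0.5. The curves are at 54.1% and 44.8%. False gap 9.3 points.

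| Median OS (months) | Dead before Week 12 (of 615) | False gap at 12 months, p = 0.5 to 0.7 | False gap at 24 months, p = 0.5 to 0.7 |
|---|---|---|---|
| 12 | 14.7% (91) | 15.1 to 21.4 | 7.5 to 10.7 |
| 18 | 10.1% (62) | 12.8 to 19.1 | 8.1 to 12.0 |
| 24 | 7.7% (47) | 10.9 to 16.6 | 7.7 to 11.7 |
| 36 | 5.2% (32) | 8.2 to 12.9 | 6.5 to 10.2 |
| 60 | 3.1% (19) | 5.5 to 8.8 | 4.8 to 7.6 |

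**Medians.** The CR/PR/SD median is m + t0. The PD/NE median is m · log2[2(1 − p)/(1 − p · S0)]. For m = 12 these are 14.8 against 6.9 to 9.6 months; for m = 18, 20.8 against 12.5 to 15.5 months. The false difference is 5.1 to 8.2 months.

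**Some early deaths have a BOR.** Unscheduled scans happen; SAP Table 4.2.4-1 has a row for "Progression documented between scheduled visits". Suppose half of the early deaths have a BOR and reach CR/PR/SD at the same rate p. The CR/PR/SD share is then A = p · [S0 + 0.5(1 − S0)], and the curves are p · S(t)/A and (1 − p) · S(t)/(1 − A). For medians of 12 to 36 months the false gap falls to 4.1 to 11.3 points at 12 months and 3.3 to 6.3 at 24. If those early scans all showed PD, it would not fall.

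**Response truly predicts survival.** Take two classes with hazards 0.3λ and λ and survival R(t) and N(t), with a share π in the better class at first dose. For π = 0.6 and overall median 24 months, λ = 0.0570 per month. The displayed curves are R(t)/R(t0) and (1 − π) · N(t)/(1 − π · R(t0)).

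- 12 months: true gap 31.0, displayed 38.2, excess 7.2 points.
- 24 months: true gap 40.9, displayed 45.7, excess 4.8 points.

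Across medians of 12 to 36 months and π of 0.5 to 0.7, the excess is 4.3 to 11.2 points at 12 months and 3.4 to 5.8 at 24.

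**Does a landmark remove it?** In 1,500 simulated null trials per scenario (615 subjects, censoring at 24 months; medians 12, 24 and 36; p = 0.5 and 0.65), the split from first dose gave average hazard ratios of 0.61 to 0.76. A Week 12 landmark gave 1.00 in all six scenarios. A further check used 1,000,000 subjects per scenario, scans spread over the ±5-day window and 20% slipping by 21 days independently of outcome. The day-89 landmark gap between CR/PR/SD and PD stayed within 0.2 points of zero in all nine scenarios.

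**The case against.** The strongest reply has four parts.

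1. **The SAP never says that a subject who dies unscanned is NE.** This is true. SAP 4.2.5 has the investigator assign NE at scheduled assessments, and no rule covers a missing BOR. If such subjects sat in neither curve, both null curves would equal S(t)/S0 and the gap would vanish in this model. But ORR is counted over all treated subjects and the split has only two groups, so PD/NE is the natural reading. The missing rule should be written down either way.
2. **Separating NE from PD would be enough.** In the simple model it would be. It is not enough where deterioration prompts an early scan showing PD, because the PD group then carries less guaranteed survival than CR/PR/SD.
3. **The null range overstates the artefact.** Response probably does go with survival, and then most of the displayed gap is real, as the hazard ratio 0.3 case shows. The shape of the hazard matters too. With S(t) = exp[−ln 2 · (t/m)^k] and the same medians of 12 to 36 months, k = 1.5 gives null gaps of 2.6 to 11.3 points at 12 months and 2.0 to 4.4 at 24. With k = 0.7 they are 15.9 to 31.0 and 13.0 to 21.0. The size moves both ways; the direction does not.
4. **It is one descriptive display in a single-arm safety study.** This limits the harm but does not remove the bias from the curves and medians.

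**Conclusion.** The concern holds. Followed as written, the plan gives a biased comparison of OS by BOR, always in favour of CR/PR/SD, provided unscanned deaths are placed in PD/NE. The direction follows from the definitions and the scan schedule.

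The size depends on early mortality, on how often early scans occur and on the true association, none of which the documents give. A reasonable statement is 8 to 21 points at 12 months if response is unrelated to survival, and 4 to 11 points on top of a real difference if it is strongly related (constant hazards, medians of 12 to 36 months). The false difference in medians is 5 to 8 months under the null where both medians fall inside the 2-year follow-up.

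The primary safety endpoint, all-treated OS, PFS, ORR and the baseline subgroups are not affected. It is worth correcting because the remedy is cheap and the display invites a strong reading.

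**What to change.** In SAP 6.4 and 7.5.2, replace the split with a landmark analysis at the close of the Week 12 window, day 84 + 5 = 89:

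- Include subjects alive and in follow-up at day 89, classified by response recorded up to that day.
- Measure OS from day 89.
- Show NE separately from PD, and state how a subject with no BOR is classified.
- Report how many died or were censored before day 89.
- Add one later landmark as a sensitivity analysis, to pick up late scans and responses first seen after day 89.

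Treating response as a time-dependent covariate is an acceptable alternative.

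The cost is SAP text and a small programming change, with no new data. Early deaths leave this one analysis: 1 − exp(−ln 2 · 2.924/m), which is 5.5% for m = 36 and 15.5% for m = 12, or about 34 to 96 of 615. Response at day 89 is not the same quantity as BOR, so the output should be labelled accordingly. Subjects scanned late count as NE, about 20% of those alive if 20% of scans slip. Protocol Table 5.1-2 (footnote a) lets procedures slip with a delayed dose, while Protocol 4.5.6 keeps tumor assessments on schedule during interruptions. Slippage may therefore not be independent of outcome, which is a further reason for the second landmark.

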7 STATISTICAL ANALYSES

SAS® version 9.4 or higher will be used for statistical analyses, tabulations and graphical presentations.

7.1 General Methods

The analysis of primary, secondary, and exploratory endpoints will be reported for all treated subjects and/or by subgroups defined in Section 6.4, unless otherwise stated in this SAP.

The CA209 Core Safety DPP refers to several analyses that are to be performed on subjects with extended follow-up. For these summaries, adverse events occurring from the time of the first dose of study therapy through 100 days after the last dose of study therapy will be summarized. Further general methods information for the safety analyses, including general methods for adverse events and laboratory tests can be found in Section 7.1 of the CA209 Core Safety SAP version 5.

7.2 Study Conduct

7.2.1 Accrual

The accrual pattern will be summarized per country, investigational site, and per month for all treated subjects. Enrollment date, first dosing date, country, investigational site will be presented in a by subject listing of accrual.

7.2.2 Relevant Protocol Deviations

The relevant protocol deviations will be summarized for all treated subjects. The following programmable deviations from inclusion and exclusion criteria will be considered as relevant protocol deviations. Non-programmable relevant eligibility and on-treatment protocol deviations, as well as significant (both programmable and non-programmable) eligibility and on-treatment protocol deviations will be reported through CTMS listings.

Eligibility at entrance:

- Subjects without histologically documented unresectable Stage III or Stage IV melanoma, as per AJCC staging system
- Subjects without measurable disease by CT or MRI per RECIST 1.1 criteria at baseline (per Investigator)
- Subject with baseline ECOG performance status > 2
- Women of childbearing potential (WOCBP) had a positive serum or urine pregnancy test at baseline

On-Study:

- Subjects receiving anti-cancer therapy (i.e., chemotherapy, hormonal therapy, immunotherapy, or standard or investigational agents for treatment of cancer) while on study therapy

A by-subject listing of relevant protocol deviations will also be produced.

7.3 Study Population

7.3.1 Subject Disposition

Subject disposition will be listed for all enrolled subjects. For subjects who are treated, the subject's gender, age, race, consent date, vial assignment date (if available), first and last dosing date, off-study date, and reason for going off-study will be listed. For subjects who enroll, but are not treated, the subject's gender, age, race, consent date, and reason for not entering the treatment phase will be listed.

Summary tables reflecting the number of subjects who are enrolled, who are treated, reasons for not entering the treatment phase, and who completed the study will be presented as overall.

The number of subjects who do not complete the study, both overall and according to reasons for discontinuation from the study, will be summarized according to the general methods.

7.3.2 Demographic and Baseline Characteristics

The following baseline characteristics will be summarized for all treated subjects, according to the general methods. All baseline presentations will identify subjects with missing measurements. Listings will also be provided.

- Age (descriptive statistics)

- Age category I (< 65, ≥ 65)
- Age category II (< 65, ≥ 65- < 75, ≥ 75)
- Gender (Male, Female)
- Race (White, Black or African American, American Indian or Alaska Native, Native Hawaiian or Pacific Islander, Asian, Other)
- Ethnicity (Hispanic or Latino, Not Hispanic or Latino, Not Reported)
- BRAF mutation status (Wild Type, Mutant, Not Reported)
- Region (EU, Australia)
- Weight (descriptive statistics)
- Height (descriptive statistics)
- Baseline ECOG Performance Status (0, 1, 2)
- Smoking status (Never Smoked, Current/Former, Unknown)
- CNS metastases (Yes, No, Not Reported)
- Treatment status of CNS metastases (Treated, Untreated)
- Subtype of melanoma
- Melanoma stage at study entry (III, IV, Unknown)
- M stage at study entry (M0, M1A, M1B, M1C with Brain Metastases, M1C without Brain Metastases, Unknown)
- Baseline LDH (≤ ULN, > ULN)
- Baseline LDH (≤ 2*ULN, > 2*ULN)
- Time from Initial Disease Diagnosis to Vial Assignment date (if available; otherwise, use first dose date) (< 1 year, 1 - < 2 years, 2 - < 3 years, 3 - < 4 years, 4 - < 5 years, ≥ 5 years)
- All lesions (Investigator Tumor Assessments at Baseline): sites of disease, number of disease sites per subject.
- Target lesions (Investigator Tumor Assessments at Baseline): Presence of target lesions, site of target lesion, sum of longest diameter of target lesion.

7.3.3 Medical History

General medical history will be listed by subject.

7.3.4 Prior Cancer Therapy

The following will be summarized by treatment group for all treated subjects, according to the general methods.

- Prior neo-adjuvant therapy (yes/no)
- Prior adjuvant therapy (yes/no)
- Time from completion of prior adjuvant therapy to enrollment (subjects who received prior adjuvant therapy), (< 6 months and ≥ 6 months)
- Prior surgery related to cancer (yes/no)
- Prior radiotherapy (yes/no)

Agents and medication will be reported using the generic name. A listing by subject will also be provided.

